### 4.2 Hypotheses

The study has been designed to address the following hypotheses:

1. A Better Start will have an impact on children's socio-emotional functioning, their nutritional status, and their language development at 3 and 7 years of age;
2. The impact of the programme will be mediated by change in parental functioning including their mental health and parenting practices;
3. A range of process factors including the level of service provision and the integrity with which such services are delivered will mediate the success of the programme.

## 5. DESIGN AND METHODOLOGY

### 5.1 Study Design and Timescale

Central to the Impact evaluation is a longitudinal study based on a series of surveys of parents and children in both intervention and matched comparison areas. It will begin in 2015, firstly with the piloting of questionnaires over a 3-month period across two of the intervention areas (Lambeth and Southend), prior to the collection of baseline data from families of 1, 2 and 3-year-olds across all intervention and comparison sites. This will generate data on all proposed parent and child outcomes (up to when the children are aged 3) prior to the implementation of *A Better Start* in the five sites. Before running the main longitudinal study, the Consortium will run a small pilot in all intervention areas and five comparison areas, to test its recruitment and early data collection methods. This will take place in 2016.

The cohort study will begin in 2019 and end in 2026. All elements of the study will be replicated in matched comparison areas to generate counterfactual estimates. During its life cycle, the study will use a wide-range of data collection methods (listed in Table 1) to track families from mid-pregnancy until the children are aged 5 years. The primary data collection methods will be face-to-face interviews undertaken by trained and experienced Ipsos MORI field researchers, either in families' homes or other place of their choice - e.g. Children's Centres – (up to age 3), followed by parental online and/or postal surveys, and in-school teacher assessments when children are 5-years of age.

The study has been designed to generate a significant amount of evidence, key elements of which are:

- Data from within programme areas will be used to measure and quantify short-, medium- and longer-term outcomes for the families who are being targeted by the interventions, and to establish how these evolve over time, from pre-programme to late programme;
- Data from within comparison areas will generate estimates of the counterfactual outcomes for matched parents and children who are not receiving the interventions, but are receiving standard services;
- For both intervention and comparison areas, the implementation data about how parents use and experience services, will generate an understanding about how any intervention impacts have been achieved;
- For both intervention areas and selected comparison areas (e.g. the closest matched comparison area per intervention area), early years services data will generate an understanding about systems change within early years provision and help us determine whether any changes detected over time are due to ABS or occur for another reason;
- Administrative data on child and family outcomes in the five ABS areas against those in other similar matched areas, will provide estimates of the impact of the programmes across the whole of the eligible population, to test whether the work of the five areas has area-wide impacts;
- Data on costs and services from the five areas will be combined with our findings on the impact of the programme, which will permit us to measure the cost-effectiveness of the programme, both overall and for each site.

The data collection within intervention and comparison areas comprises two components:

1. Cross-sectional, baseline surveys of parents of 1, 2 and 3 year-olds in the first year of the programme (2016/17), which will provide baseline data on outcomes for current parents and children in all our areas prior to the implementation of A Better Start. Baseline surveys will be conducted in both intervention and matched comparison areas, allowing us to (a) check that the intervention and comparison areas are the same prior to the start of the programme; and (b) to allow us to measure changes in outcomes over time in both the intervention and comparison areas.
2. A large cohort study, starting recruitment in 2019, which will generate data on impact. Families will be tracked until the children are 5-years of age. In addition to parent and teacher-report data, we will collect additional data for a sub-sample of families, using measures that will provide valuable information, but which are too costly to collect and/or process across the entire sample.

### 5.1.1 Potential Additional Data Collection

During both the recruitment pilot and the baseline study, ethical approval permits the team to request consent to hold mothers' contact details for 12 months after the initial interview. This allows the field team to make contact with them again should further research prove valuable.

It is made clear in both the pilot and baseline studies that providing consent for re-contact at this stage does not lead to any obligation or expectation that mothers will take part in any future study, or that any further contact will necessarily take place.

### 5.1.2 Areas and Timelines

During the baseline survey (2016/17) and cohort study (January 2019 - 2026), data will be collected from:

- 5 intervention areas
  - **Blackpool** (wards: Brunswick; Talbot; Claremont; Bloomfield; Clifton; Park; Victoria);
  - **Bradford** (wards: Bradford Moor; Little Horton; Bowling & Barkerend);
  - **Lambeth** (wards: Stockwell; Tulse Hill; Vassall; Coldharbour);
  - **Nottingham** (wards: Arboretum; St Anne's; Bulwell; Aspley);
  - **Southend** (wards: Milton; West Shoebury; Westborough; Shoeburyness; Victoria; Kursaal)
- 13 comparison areas (3 per programme area):
  - BLACKPOOL COMPARATORS**
    - **Barnsley** (wards: North East; Stairfoot; Dearne South; Worsbrough; Monk Bretton; St Helens; Dearne North)
    - **Stoke-on-Trent** (wards: Joiner's Square; Burslem Central; Blurton West & Newstead; Meir South; Hollybush & Longton West; Meir North; Bentilee & Ubbertley)
    - **Plymouth** (wards: Moor View; Efford & Lipson; St Duseaux; Ham; Devonport; St Peter & the Waterfront; Honicknowle)
  - BRADFORD COMPARATORS**
    - **Coventry** (wards: Binley & Willenhall; Foleshill; Longford)
    - **Derby** (wards: Sinfin; Normanton; Arboretum)
  - LAMBETH COMPARATORS**
    - **Islington** (wards: Junction; Tollington; Hillrise; Holloway)
    - **Hackney** (wards: Cazenove; Lordship; Queensbridge; Stoke Newington Central)
    - **Hammersmith and Fulham** (wards: Askew; Shepherd's Bush Green; College Park & Old Oak; Wormholt & White City)
  - NOTTINGHAM COMPARATORS**
    - **Hull** (wards: Bransholme East; Ings; Newington; Pickering)
    - **Southampton** (wards: Bevois; Coxford; Redbridge; Bitterne)
    - **Birmingham** (wards: Billesley; Kings Norton; Bartley Green; Springfield)
  - SOUTHEND COMPARATORS**
    - **Sefton** (wards: Cambridge; Duke's; Ford; Kew; Netherton & Orrell; Norwood)
    - **Portsmouth** (wards: Hilsea; Fratton; Cosham; Nelson; Paulsgrove; Charles Dickens)

Table 1 provides both an overview of data collection methods at each study time-point, and of the timeline for both the baseline and cohort studies.

**Table 1. Summary of main evaluation timeline, data collection methods and time-points**

Year	Stage involved	Mother / main carer	(Brief resident) Partner Q'aire	Additional assessments
BASELINE DATA COLLECTION				
2016/17	Baseline	Face-to-face interview of families with children of ages 1,2 & 3	x	x
2016/17 PILOT PARTICIPANT IDENTIFICATION & RECRUITMENT METHODOLOGY				
	26-36 weeks' pregnant	Face-to-face interview	✓	x

	Baby aged 2-months	Short online or postal survey	x	x
	Baby aged 4-months 	Short telephone interview or online survey	x	x
COHORT STUDY				
2019/20	26-36 weeks' pregnant	Face-to-face interview	✓	x
2019/20	At birth		x	Hair Sample from mother (to measure cortisol)
2019/20	Baby in first week of life		x	Cheek (Buccal) Swab (for epigenetic purposes)
2019/20	Baby aged 4-months	Short telephone interview or online survey	x	x
2020/21	Child aged 1	Face-to-face interview at home	✓	CARE Index (video clip of child playing to assess parent-child interaction)
2021/22	Child aged 2	Face-to-face interview at home	✓	From the child: both hair sample (cortisol) and a cheek swab (to measure epigenetic changes)
2022/23	Child aged 3	Face-to-face interview at home	✓	
2024/25	Child aged 5	Postal or online survey Schools Data	x	video-recorded MCAST measure of child attachment – carried out in school by trained researcher

## 5.2 Questionnaires

Questionnaires have been designed to include validated and adapted measures, and bespoke questions to assess primary and secondary child and parental outcomes. Survey time-points include the following: 26-36 weeks antenatal; 4-months postnatal; ages 1, 2, 3 and 5.

The main types of data will be collected as follows:

### 5.2.1 ABS Programme Services data: pathways and connectivity

To understand the degree to which systems change may have occurred within programmes, there is a requirement to understand the early years system and how it operates in each area at the beginning and throughout the lifetime of the ABS programmes. The evaluation must also be able to compare with areas that have not had the benefit of the ABS programme, to provide an understanding whether any changes detected are due to ABS or have occurred for another reason. This will involve undertaking a mapping exercise of antenatal and early years services in the five ABS areas and five of the (most closely matched) comparison areas.

The research team will contact relevant lead professionals in a range of antenatal and early years services, such as midwifery, health visiting and Children's Centres, to collect some simple data on the structure of services in this area. This information may be collected via a short questionnaire, a telephone interview or a face-to-face interview, depending on the type of information we are requesting.

### 5.2.2 Parent-Report Data

The survey questionnaires will comprise a number of demographic questions, and standardised and validated self-report questionnaires to assess a range of aspects of parental and child wellbeing including self-report measures of mental health; substance use; and domestic violence.

 Schedule permitting, i.e. where local R&D approval has not been issued as quickly as expected, it may only be possible to follow-up participants in these areas to the 26-36 weeks' gestation or 2-month postnatal time-point, rather than to 4-months postnatal as originally intended.

### 5.2.3 Teacher-Report Data

Teachers will be invited to complete teacher report versions of measures of children's social and emotional functioning (e.g. Strengths and Difficulties Questionnaire) at 5 years.

### 5.2.4 Child-Report Data

Children will take part in a number of assessments of their language at different ages using a range of standardised measures (e.g. Bayley Scales at 12 months; British Ability Scales at 3 years); a measure of their attachment at 5-years in which they are invited to complete the Manchester Child Attachment Story Task in school; a measure of their self-esteem and feelings about school (All About Me Questionnaire).

### 5.2.5 Objective Data

We will in addition collect the following objective measures of outcome:

Non-invasive biometric measures include the following:

- Mother's hair sample to assess cortisol levels at or around the time of birth - subsample
- Baby buccal (cheek) swab to assess epigenetics at or around the time of birth and again at age 2 - subsample
- Child hair sample and buccal swab at 2 years – subsample.

Other objective non-biological measures include the following:

- Height and weight – full sample at all time points post-delivery
- 3-minute videotape recording of parent-infant interaction at 12 months (CARE Index) – subsample only
- Home learning environment at 3 years – full sample
- Manchester Child Attachment Story Task (MCAST) measure of attachment at 5 years – subsample only

### 5.2.6 Administrative Data

There will be several points in the study where we ask participants to consent to their data being linked to other existing health, education and social care data:

- When participants sign up for the study they are asked for their consent to give permission to use the birth records of their child. This will provide information about the weight of the baby, type of delivery and gestation period of the pregnancy;
- Participants will also be asked at this time if they will consent to the evaluation team receiving identifiable service use data from the ABS intervention sites lead organisations (e.g. nature and extent of participation in service interventions such as Family Nurse Partnership, Bumps for Babies etc.). A data sharing agreement will exist between the evaluation team and each of the service providers;
- After the first interview when the woman is 26-36 weeks' pregnant she will be asked for permission to use her NHS number to link to her Hospital Episode Statistics records. This will provide information on hospital inpatient, outpatient and day case admissions throughout the period of follow-up;
- After the first interview, when the woman is 26-36 weeks' pregnant, she will also be asked for her permission to access her child's ASQ3 data. This is an Ages and Stages Questionnaire – a child development rating scale, which will be collected from 2015 onwards as part of a child's assessment at the age of 2 years. The ASQ3 is being collected as a Public Health Outcome indicator and Local Authorities will report the data to a central point before it is published, most likely by CHIMAT.
- When the child reaches three years old the mother will be asked as part of the face-to-face interview if we can link her child's information to their school records using the National Pupil Database. If she agrees, we shall ask the name of the school in the 5 year olds' postal questionnaire
- Administrative data on the educational progress of cohort children will be gathered at ages 5 and 6 years from the Pupil Level Annual Schools Census or PLASC. At the time of writing, this would include:
  - The phonics test administered in schools at age 6
  - Early Years Foundation Stage Profile (EYFSP) results at age 5, although these are now due to be withdrawn. If equivalent tests are reinstated then these data will be used instead. If they are not, alternative reliable standardised tests will need to be used.

In this event, an amendment to the ethics application would be submitted with full details, once known.

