#### *Informed Consent for the School-based Data Collection*

Parents will be asked at the age 3 interviews for details of the school likely to be attended by their child, and for consent for the research team to contact the school. Parents who do not know the child's intended school at age 3 will be asked for consent to be re-contacted at age 4 in order to obtain this information. Consent for data collection at age 5 will also be obtained at this time (i.e. at age 3 where parents know the school, at age 4 when they do not). However, since this will represent the last point of direct contact with parents, parental consent for data collection at age 6 will be obtained via teachers in the schools at the time of the age 5 teacher survey.

The evaluation has been designed to predominately follow the progress and outcomes of the child. If a child taking part in the evaluation were subsequently removed from the care of the mother, or the mother dies etc., then informed consent would be sought from the child's primary carer or guardian to continue in the evaluation.

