### 5.5.2 Main Cohort Evaluation Surveys

The primary research question will be addressed using a longitudinal cohort study in which a target of 2,885 pregnant women across the five intervention and fifteen matched comparison areas will be recruited to the study. Further detail is provided in Table 2.

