**Table 2. Cohort Survey Sample Sizes**

Survey Time Point	ABS (Programme) Area	Comparison (Matched Control) Areas
26-36 weeks' antenatal	1715	1170
Child Aged 1 Year	1200	825
Child Aged 2 Years	1060	720
Child Aged 3 Years	815	555

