### 5.5.3 Sample Size Justification

The sample size for the cohort study has been set with the primary aim, after attrition, of generating 815 interviews with parents of three year olds in programme areas and 555 in comparison areas. The 'headline' estimates of impact will be based on difference-in-differences estimates. That is, change since baseline for children of the same age group in ABS areas, minus change since baseline in comparison areas. For outcomes at age 1, for instance, this will be based on the four sets of data within the second row of the table (i.e. 500; 270; 1200; 825). Samples of this size will enable detection of effect sizes of 0.25 standard deviations (with 80% power). For binary outcomes, this equates to being able to detect an impact of around 12 percentage points (i.e. if 12% of children in ABS areas have a better outcome at age 1 as a direct result of the programme, a difference-in-difference estimate should be observed that is significantly different to zero). At Age 2 the cohort sample sizes will have been subject to attrition, and the detectable effect size at age 2 will be just over 0.25; and with further attrition at Age 3, the detectable effect size will be 0.26.

In practice, it is hoped that no real differences in the baseline outcomes for ABS and comparison areas will be observed. If baseline differences can be ruled out, then the evaluation can focus on comparing the ABS and comparison cohort samples. This will greatly improve the statistical power. For example, at age 1, if only the two cohort samples of 1200 and 825 were compared, effect sizes of 0.13 standard deviations could be detected.

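### School-record linkage consent is first sought at the age-3 interview, when the plan expects 47.5% of recruits to remain, which needlessly limits the sample for the EYFSP and phonics outcomes

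*Protocol*

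**What the plan says.** Section 5.2.6 (Administrative Data) of the protocol sets a time for each linkage request.

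- **Birth records and ABS service use:** at sign-up.
- **Hospital records:** "After the first interview when the woman is 26-36 weeks' pregnant she will be asked for permission to use her NHS number". The child's ASQ3, which is not collected until age 2, is requested at the same stage.
- **School records (National Pupil Database):** "When the child reaches three years old the mother will be asked as part of the face-to-face interview if we can link" the child's information to school records. The next step is "If she agrees, we shall ask the name of the school in the 5 year olds' postal questionnaire".

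No earlier request for education linkage appears. The data-linking item in Section 5.7.4 covers health and social care records only.

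Section 5.4.6, on consent for the school-based data collection, gives a partly different route: "Parents will be asked at the age 3 interviews for details of the school likely to be attended by their child". Parents who do not yet know the school are re-contacted at age 4. Consent for age-6 data collection is then obtained through teachers at the time of the age-5 survey.

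Section 5.7.2 lists EYFSP at 5 and the Year 1 phonics test at 6 under the primary outcome measures. Section 5.2.6 draws both from administrative data and adds that EYFSP may be withdrawn and replaced.

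On numbers, Section 5.5.2 sets "a target of 2,885 pregnant women across the five intervention and fifteen matched comparison areas will be recruited to the study", and Section 5.5.3 aims at "generating 815 interviews with parents of three year olds in programme areas and 555 in comparison areas".

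**The concern.** Collecting an outcome from school records needs consent and a match, but no interview. Under the plan, a family not interviewed at age 3 is never asked, so the linked sample starts from the families still in the study at that point. Two consequences follow.

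1. **Precision.** EYFSP and phonics would be analysed on fewer than half of those recruited. Part of that loss comes only from when the question is asked.
2. **Bias.** If families lost before age 3 differ in their children's school outcomes, and differ in another way in programme areas than in comparison areas, the linked estimates carry that selection.

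The protocol's own practice shows that asking earlier is feasible, since it requests the age-2 ASQ3 before the child is born. It gives no reason for treating school records differently. Families lost before age 3 cannot be asked afterwards, so the choice has to be settled before recruitment.

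**Working it through.** **Inputs**

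- Antenatal sample: 1,715 programme and 1,170 comparison, total 2,885 (Table 2).
- Age-3 sample: 815 and 555, total 1,370 (Table 2, Section 5.5.3).
- Power: 80% (Section 5.5.3). Two-sided alpha of 0.05 is assumed; the section states none.
- Consent rate, share excluded by design and area ICC: not given. The values below are assumptions.

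**Formula.** Detectable effect in SD units = (1.960 + 0.842) × √(sum of 1/n) = 2.8016 × √(sum of 1/n).

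**Reproducing the plan's figures**

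- Age 1, cohort only, 1,200 v 825: 2.8016 × √(1/1200 + 1/825) = 0.127. The plan states 0.13.
- Age 1, difference-in-differences with 500, 270, 1,200 and 825: 0.247. The plan states 0.25.
- Age 3, with 500, 270, 815 and 555: 0.262. The plan states 0.26.

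The formula and alpha therefore match the plan's own. Its figures carry no allowance for clustering.

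**Planned loss before the question is asked.** 1,370/2,885 = 47.5% remain, so 52.5% are lost. By group: 815/1,715 = 47.5% and 555/1,170 = 47.4%.

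**Cohort-only detectable effect, full consent, independent children**

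- Plan: 2.8016 × √(1/815 + 1/555) = 0.154 SD.
- Antenatal ceiling: 2.8016 × √(1/1715 + 1/1170) = 0.106 SD.

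The ceiling cannot be reached. Section 5.4.3 excludes families who move away and women without a live birth, and families may withdraw.

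**Realistic comparison.** Assume 80% consent by either route, and 10% to 30% of recruits excluded by design on the antenatal route. The 1,370 is treated as already net of exclusions.

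| Route | Linked n, programme / comparison | Independent children | Area ICC 0.01 |
|---|---|---|---|
| Plan, 80% consent | 652 / 444 | 0.172 | 0.226 |
| Antenatal, 10% excluded | 1,234.8 / 842.4 | 0.125 | 0.193 |
| Antenatal, 30% excluded | 960.4 / 655.2 | 0.142 | 0.204 |

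The last column uses 2.8016 × √[0.99 × (1/n1 + 1/n2) + 0.01 × (1/5 + 1/13)], with the 5 programme and 13 comparison areas listed in Section 5.1.2. For the plan: 0.99 × 0.003786 + 0.002769 = 0.006517; its square root is 0.0807; the result is 0.226. At full consent the same formula gives 0.213 for the plan and 0.181 for the antenatal ceiling.

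The reduction in detectable effect is 18-27% with independent children (1 − 0.1420/0.1724 and 1 − 0.1252/0.1724). With the ICC it is 10-15% (1 − 0.204/0.226 and 1 − 0.193/0.226).

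**Break-even.** Usable antenatal linkage would have to fall to 1,370/2,885 = 47.5% of recruits to do no better than the plan with everyone consenting. Against the plan at 80% consent the figure is 1,096/2,885 = 38.0%.

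**The postal step.** If linkage also needs the school name from the age-5 form, an assumed 60-90% response leaves 28-43% of recruits. At full consent the plan's detectable effect then becomes 0.199-0.163 SD.

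**The case against.** The strongest objections concern how much the change would recover.

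- **Part of the loss is not recoverable.** Movers and women without a live birth are excluded by Section 5.4.3, consent can be withdrawn at any time, and some will refuse linkage. This stands. A reader might take 0.106 SD as the gain on offer, and the documents do not support that.
- **Clustering shrinks the gain.** With a small number of areas, the between-area term does not depend on when consent is asked. This stands, and it is why the ICC column is shown.
- **Bias is not shown.** A reader might infer that the age-5 and age-6 estimates are biased. Planned retention is almost equal by group (47.5% v 47.4%), and Section 6.2 says that non-response weighting will be considered. Equal retention does not rule out a difference in who is lost, but only a risk can be claimed.
- **School records are not uniquely protected from attrition.** A reader might think they are the only outcomes obtainable for families who drop out. Birth records, hospital records and ASQ3 are also consented early, and they already allow some check on who is lost. Section 5.1 also plans area-level administrative comparisons that do not depend on cohort retention.
- **Moving one item is not enough.** The age-5 postal request for the school name and the teacher route for age-6 consent would remain. This stands, and the fix must cover both.
- **The age-5 measure is unsettled.** EYFSP may be replaced, so antenatal consent would have to cover a successor test. The phonics test is not affected.

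A reader might also count the absence of a survey baseline at ages 5 and 6 against the plan here. That is a separate matter, and Section 6.2 leaves the choice of datasets to compare to each phase's analysis plan.

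**Conclusion.** The point holds as a worthwhile and inexpensive improvement. It is not a contradiction in the protocol. First asking for school-record linkage at age 3 confines two outcomes listed as primary to at most 1,370 of 2,885 recruits, although the protocol asks for comparable permissions before birth.

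The loss of precision follows from the planned sample sizes. At 80% consent and 10-30% excluded by design, the detectable effect would fall from 0.172 to about 0.125-0.142 SD with independent children, or from 0.226 to about 0.193-0.204 SD with an area ICC of 0.01. The consent rate, the excluded share and the ICC are all assumptions, and the 52.5% loss is planned, not observed. Propensity matching and weights are ignored, so the absolute values are optimistic.

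The gain is confined to linked-record outcomes. The age-5 parent survey, the teacher questionnaire and the attachment task still need live contact.

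**What to change.** 1. In Section 5.2.6, request National Pupil Database linkage at the antenatal interview, beside the NHS-number and ASQ3 permissions. Word it to cover any replacement for EYFSP. Re-ask or re-affirm it at ages 1, 2 and 3.
2. Amend Section 5.2.6 so that linkage does not depend on the school name from the age-5 postal questionnaire. Reconcile this with Section 5.4.6, which collects school details at age 3 or 4.
3. State in Section 5.4.6 whether consent through teachers for age-6 data applies to the linked phonics result. If it does, reconcile it with the linkage consent.
4. Define the EYFSP and phonics analysis set as all children with linkage consent who are still eligible under Section 5.4.3, whether or not the family was interviewed at age 3.

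The cost is an ethics amendment, revised consent materials and edits to two sections. The main drawback is that consent is given before birth and has to be re-affirmed, which cannot be done for families lost early. The ethics submission should say how their consent stands.
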